5.4.2 Specific objectives

1. To compare uptake of voluntary medical male circumcision between the RITE intervention and the standard of care among men attending Bwaila STI clinic in Lilongwe Malawi
 - a. To compare time-to-uptake of voluntary medical male circumcision between the RITE intervention and the standard of care among men attending Bwaila STI clinic in Lilongwe Malawi
 - b. To assess factors affecting uptake of voluntary medical male circumcision among men attending Bwaila STI clinic in Lilongwe Malawi
2. To develop STI clinic setting-specific voluntary medical male circumcision educational material at Bwaila STI clinic in Lilongwe Malawi
3. To assess the acceptability, appropriateness and feasibility of the RITE intervention among men and healthcare workers at Bwaila STI clinic in Lilongwe, Malawi.

- a. To assess the acceptability and appropriateness of the RITE intervention among men at Bwaila STI clinic in Lilongwe, Malawi

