6.2 Study setting

The study setting is the Bwaila STI Clinic (BSC) and Bwaila VMMC clinic at Bwaila District Hospital (BDH). BDH is a public secondary level facility in Lilongwe and the only facility offering specialized STI care situated in a busy central town area of the Lilongwe district. Approximately 80 patients visit BSC per day. The VMMC clinic and BSC are about 300 meters apart within the BDH campus. Twenty (20) people comprising nurses, clinicians, HIV testing services (HTS) counsellors, receptionists and support staff run BSC. As standard of care, all STI patients at BSC receive group health education (GHE) and are offered opt-out provider initiated HIV testing as standard of care, before receiving care for their STIs. We propose to integrate intensified health education to the GHE. About two to three GHE sessions are conducted per day with different cohorts of patients based on their time of arrival at the clinic however only one GHE includes education on VMMC. The clinic receptionist assisted by a nurse or counsellor conducts GHE. The first GHE session includes a mobilizer from the VMMC clinic who conducts an educational talk on VMMC every morning at the STI clinic and refers men to the VMMC clinic using referral slips. The additional GHE sessions do not have educational talks by the mobilizer. We will train the clinic receptionist, counselors, nurses and the mobilizer to conduct intensified health education. As standard of care, uncircumcised men with STIs are supposed to be offered VMMC at the STI clinic by clinicians however this is not reinforced. Data on demographics, HIV testing and treatment, sexual history and STIs are collected routinely through an electronic medical registry.

The VMMC clinic has a director, administrator, program officers, clinicians (male and female), nurses (both male and female), data clerks, mobilizers and support staff. A team consisting of one clinician, an assisting nurse and other support staff conduct circumcisions. Circumcisions are

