done at the VMMC clinic and in the community through outreach clinics and mobile vans. Data such as demographics, referral source, date and outcome of VMMC are recorded in registers. We will use these registers to track men referred from the STI clinic who will undergo circumcision. Men attending the STI clinic may either be index cases (symptomatic) or sexual partners (symptomatic or asymptomatic). Men with symptomatic STIs will not undergo VMMC on the same day of their STI clinic visit until they complete treatment for their current STI.

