6.6.1 Composition

The RITE intervention has been guided by the conceptual framework (figure 1) and Powell et al's refined compilation of implementation strategies [32].

Intensified Health Education (I)

Intensified health education will be more consistent and setting-specific education on VMMC incorporated into the routine STI/HIV health education provided at Bwaila STI clinic.

Currently, health education on VMMC at Bwaila STI clinic is offered once in the morning session – leaving out patients who come later to the clinic. The health education session combines education on HIV and STIs, usually offered by HIV testing counselor or clinic receptionists, and education on medical circumcision, offered by a VMMC mobilizer from the Bwaila VMMC clinic.

In this PhD study, we intend to make health education more setting specific and delivered better by conducting formative research to understand the views of men on VMMC with emphasis on men accessing STI care. In addition, we intend to intensify the education by conducting additional (more than one educational talk as per current standard) educational talks. The health talks will be delivered at Bwaila STI clinic – the recruitment point. The current format of the educational talks will be maintained but in addition, educational material on medical circumcision will be developed based on results from the formative research. The VMMC

mobilizer including the clinic receptionist and counselors will be trained on the educational material. We anticipate that the content of the health talk may involve the following fundamental information: description of VMMC, medical benefits of VMMC and addressing myths and misconceptions around VMMC among other topics. After the group education, men will be asked of their interest in circumcision individually by counsellors (during standard HIV testing) and clinicians as they receive care at the STI clinic.

Clinic Escorts (E)

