Uptake will be calculated as a proportion - the number of men who will undergo VMMC divided by the number of uncircumcised men offered VMMC at the STI clinic. Uptake will be calculated for each implementation block. Uptake for each block will be compared against SOC using Student's T-test at $\alpha=0.05$ significance level and 95% confidence interval, assuming normal distribution.

Objective 1a: To compare time-to-uptake of voluntary medical male circumcision between the standard of care and intervention period among men attending Bwaila STI clinic in Lilongwe Malawi

Time-to-uptake of VMMC will be calculated as the number of days taken for an individual to undergo circumcision at the VMMC clinic from the day they were offered circumcision at the STI clinic. To compare time-to-uptake between SOC and the intervention blocks, we will conduct time-to-event analysis to estimate duration to circumcision and Kaplan Meier curves will be plotted and compared between SOC and implementation blocks. We will also study factors affecting time-to-uptake using cox regression.

Objective 1b: To assess factors affecting uptake of voluntary medical male circumcision among men attending Bwaila STI clinic in Lilongwe Malawi

We will assess factors affecting uptake of VMMC using logistic regression modeling. We will use univariate models to assess association. Covariates with $P<0.05$ and those based on expert knowledge of this topic will be fit into multivariate logistic regression models to control for confounders.

Objective 2: To develop STI clinic setting-specific voluntary medical male circumcision educational material at Bwaila STI clinic in Lilongwe Malawi

We will use thematic analysis approach for qualitative analysis of the consultative meeting notes. The notes will be coded and salient themes will be identified. The content and delivery methods will be deduced from the salient themes.

Objective 3: To assess the acceptability, appropriateness and feasibility of the adaptable RITE intervention among men and healthcare workers at Bwaila STI clinic in Lilongwe, Malawi.

We will use mixed methods to assess acceptability, appropriateness and feasibility. For acceptability, appropriateness and feasibility quantitative surveys, these outcomes will be

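### Uptake and time-to-uptake count only men offered VMMC, a group that the education component can itself change, so comparisons of each block with standard of care may not compare like with like

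*Combined protocol and SAP*

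**What the plan says.** Under Data Analysis, Objective 1 (within section 6.3, Sample Size Calculation and Justification), uptake is "the number of men who will undergo VMMC divided by the number of uncircumcised men offered VMMC at the STI clinic". The planned comparison is: "Uptake for each block will be compared against SOC". Time-to-uptake also starts on the day of the offer (section 4, Definitions; Data Collection and Data Analysis, Objective 1a).

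Objective 1 in section 5.4.2 is set for a wider group: "To compare uptake of voluntary medical male circumcision between the RITE intervention and the standard of care among men attending Bwaila STI clinic". Study population describes uncircumcised men aged 18 or over accessing STI care. The sample size section expects at least 2280 uncircumcised men to be exposed and observed for uptake.

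On current practice, Study setting says that "uncircumcised men with STIs are supposed to be offered VMMC at the STI clinic by clinicians however this is not reinforced". It reports two to three group health education (GHE) sessions a day, "however only one GHE includes education on VMMC". Section 6.6.1 describes intensified health education as "conducting additional (more than one educational talk as per current standard) educational talks", after which "men will be asked of their interest in circumcision individually by counsellors" and by clinicians. Under Full implementation in section 6.6.2, this component starts in block one and stays in every later block. It is absent from SOC.

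**The concern.** A man enters the uptake denominator only if he is offered VMMC, and the offer is made after the period's procedures have begun to act on him. SOC and the blocks differ in the activities that lead to an offer. The proportion of men offered, and the kind of men offered, could therefore change when block one starts.

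The Objective 1 uptake comparisons are all block against SOC, which is where such a change would fall. If it happens, a difference in uptake mixes two things: more or fewer men being circumcised, and a different set of men being counted. Time-to-uptake has the same weakness, because men never offered are outside its risk set. Contrasts between blocks are less exposed, since the education component is in all four, but they are not planned for uptake.

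No planned analysis repairs this. The Objective 1 comparison is unadjusted. The logistic and Cox models are there to study factors, and they cannot bring back men who were never offered. The limitations section mentions selection by block in general terms, without selection through the offer and without a remedy.

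**Working it through.** **1. The plan's own figure.** The sample size section gives 27 men per day and a circumcision prevalence of 28%.
- 27 × (1 − 0.28) = 19.44, rounded down to 19 per day.
- 380 per month implies 380 / 19 = 20 clinic days.
- 19 × 20 × 6 months = 2280.

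The figure reproduces exactly and counts uncircumcised attenders. It contains no offer fraction, so it is not built on the Objective 1 denominator.

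**2. How the denominator enters.** Let p be circumcisions per attender and f the fraction of attenders offered, with every circumcised man among those offered. Uptake among men offered is p / f, so

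ratio among men offered = ratio among attenders × (f_SOC / f_block).

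The two ratios agree only when the offer fractions are equal.

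**3. Illustration. All rates are assumed**, because the documents give no offer or uptake rate. Take a true doubling, p = 4% under SOC and 8% in the block, with 380 attenders per period (19 × 20, a four-week block). Power is the chance of a significant result in favour of the block, from a two-sided 5% test of two proportions with pooled null variance. At these sizes that is close to the planned t-test.

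On attenders: pooled rate 0.06; null SE = √(0.06 × 0.94 × 2/380) = 0.0172; alternative SE = √((0.04 × 0.96 + 0.08 × 0.92)/380) = 0.0172; power = Φ((0.04 − 1.96 × 0.0172)/0.0172) = 64%.

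On men offered:

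| Offered, SOC | Offered, block | n | Uptake | Ratio | Power |
|---|---|---|---|---|---|
| 0.95 | 1 | 361 v 380 | 4.2% v 8.0% | 1.90 | 57% |
| 0.8 | 1 | 304 v 380 | 5.0% v 8.0% | 1.60 | 34% |
| 0.8 | 0.8 | 304 v 304 | 5.0% v 10.0% | 2.00 | 65% |
| 0.5 | 1 | 190 v 380 | 8.0% v 8.0% | 1.00 | 2.5% |
| 0.8 | 0.7 | 304 v 266 | 5.0% v 11.4% | 2.29 | 80% |

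The same true effect can look nearly intact, vanish, or be exaggerated.

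**4. Who is newly offered also matters.** Suppose that wider offering (0.5 to 1) is the only effect, men already offered respond at 8%, and unoffered men are not circumcised. Attender uptake starts at 0.5 × 8% = 4%. If newly offered men respond at 4%, 8% or 12%, attender uptake becomes 0.5 × 8% + 0.5 × r = 6%, 8% or 10%, a rise every time. Uptake among men offered goes from 8% to 6%, 8% or 10%: a fall, no change, or a rise.

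**The case against.** Uptake among men offered is a legitimate step in a care cascade. Offering under SOC need not be low: the problem statement (section 5.2) says national guidelines call for an offer to every uncircumcised male STI client, and Study setting describes a daily talk with referral slips as well as the clinician's offer. With near-complete SOC offering the distortion is small, as the 0.95 row shows. The plan may intend every uncircumcised attender to be offered. The term may also be defined on the study form (Appendix 3), whose body is not in the text available. All of this stands, and it limits how strongly the point can be put. It does not remove it: a denominator that one period's activities can alter is still the only one planned for the Objective 1 comparison.

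A reader might infer four stronger things that the documents do not support:
- **SOC reaches only a third to a half of men, because one session in two or three covers VMMC.** Session counts are not offer rates, and clinicians may offer at other times.
- **The bias works against the intervention.** If offers in the blocks were logged mainly for interested men, it would favour the intervention.
- **The present numerator is faulty.** Study setting says: "We will use these registers to track men referred from the STI clinic who will undergo circumcision". Under the current definition men never offered belong outside the numerator too. The gap would matter mainly if the denominator were widened without widening the tracking.
- **Every uptake analysis is affected in this way.** Objective 1b is a regression on factors and is not a comparison of block with SOC.

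**Conclusion.** The point holds as a risk that the plan creates and does not guard against. Uptake and time-to-uptake rest on men offered, the stated objective concerns men attending, and the education component can change who is offered between SOC and every block. That offering will in fact change is an inference from the description of the two periods.

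Size and direction cannot be derived from the documents. Under the assumed true doubling, the ratio among men offered ranges from 1.00 to 2.29 over the offer fractions shown, and power from 2.5% to 80%, against 2.00 and 64% on attenders. Equal offering leaves the ratio unchanged. This should be corrected before SOC observation starts, because men not offered and not recorded in that period may be impossible to recover later. It does not show that the study's result would be wrong.

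**What to change.** 1. **Uptake.** Under Data Analysis, Objective 1, compare each block with SOC on men circumcised divided by all eligible uncircumcised men aged 18 or over attending in that period. Count each man once, at his first eligible visit. Make this the main uptake measure and keep uptake among men offered beside it as a cascade measure.
2. **Time-to-uptake.** Start the clock at that same visit, for the same men.
3. **Offers.** Use one definition of an offer in all periods, saying whether the morning talk with referral slip, the clinician's offer and the question about interest each count. Report attended, offered, referred and circumcised per period.
4. **Data.** From before SOC observation starts, record circumcision status and visit date for male attenders. Match them by study code to the VMMC registers, beyond those referred, so that the numerator fits the new denominator. A code is needed because Ethical Considerations rules out identifiable study data.
5. **Consent.** Inclusion Criteria and Ethical Considerations require consent. State whether men who do not consent are counted, apply the same rule in every period, and obtain ethics agreement if their routine records are to be linked.

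If individual linkage is impossible, male attendances × (1 − circumcision prevalence) gives an approximate denominator for uptake only; the limitations section already plans to measure that prevalence. On the plan's figures, 27 × 20 × (1 − 0.28) = 389 per month. Prevalence five points lower or higher gives 416 or 362, about 7% either way. This would not supply a risk set for time-to-uptake.

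The cost is revised wording, some extra recording by the existing data clerks, register matching, and possibly an ethics amendment. Reported uptake percentages will be lower wherever some attenders are not offered.

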4 DEFINITIONS

Acceptability: the perception among men and healthcare workers that the adaptable RITE intervention is agreeable, palatable and satisfactory.

Appropriateness: the perceived fit of the adaptable RITE intervention to address the problem of low uptake of VMMC among men and healthcare workers.

Clinic escort: the act of escorting/accompanying a participant interested in VMMC from the STI clinic to the VMMC clinic to ensure linkage to care.

Contamination: a situation where the study population become exposed to more than one intervention component

Feasibility: the extent to which the adaptable RITE intervention will be successfully carried out at Bwaila STI clinic.

Intensified health education: consistent and setting-specific education on VMMC incorporated into the routine STI/HIV health education provided at Bwaila STI clinic.

Interference: a scenario where other stakeholders implement an intervention(s) aimed to scale-up the uptake of VMMC at the study sites which may affect attribution.

Seasonality: periodic variation in the uptake of VMMC with calendar time

SMS reminder tracing: the act of reminding participants with a VMMC appointment about their date of procedure through short messaging service.

Time-to-uptake: the number of days from the day a participant is offered VMMC to the day they undergo VMMC

Transport reimbursement: refunding money used for transportation to Bwaila district hospital for participants who undergo VMMC using standard Malawi government rates.

Uptake: the action of undergoing VMMC.

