Clinic escorts will be the act of escorting/accompanying a participant interested in VMMC from the STI clinic to the VMMC clinic to ensure linkage to care. We propose to use clinic escorts who will accompany men interested in VMMC from the STI clinic to the VMMC clinic to ensure that men are not lost in transit. Men may either undergo same day VMMC (if asymptomatic) or have an appointment for VMMC on a later date if symptomatic or if they have other viable reasons. Escorting patients is beneficial in linkage and retention in care and is policy in varied clinical settings [32]. Clinic escorts will be data clerks and clinic aides.

SMS Tracing (T)

SMS reminder tracing will be the act of reminding participants with a VMMC appointment about their date of procedure through short messaging service. This PhD study proposes to use SMS tracing to remind men who could not have same day VMMC of their appointment for VMMC. The content and frequency of the SMS messages will be guided by the findings from formative research however we have included a modifiable guide of the messages. Cell phone tracing is also a proven strategy for minimizing loss to follow-up and improving retention [33–35]

Transport Reimbursement (R)

Transport reimbursement will be refunding money used for transportation to the Bwaila district hospital for participants who undergo VMMC using standard Malawi government rates.

Transport reimbursement equivalent to US\$10 as stipulated by the National Health Sciences Research Ethics Committee (NHSRC) in Malawi, will be offered to all men who will undergo VMMC on the day of the procedure to minimize the opportunity cost. Incentives also have been shown to improve many medical outcomes [40, 41]. Eligible men will receive transport reimbursement when they undergo VMMC. Men who cannot have same day circumcision will receive a coupon to present on the day of the procedure for reimbursement. Documentation of the VMMC procedure will be confirmed in the VMMC clinic's procedures register before payment.

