This will be full roll-out of our intervention. The intervention will have four implementation blocks (Appendix 1) that will be different combinations of the intervention components in an incremental manner. There will be one week of no intervention between interventions as a wash-out period. The implementation will be as follows: First we will observe the SOC VMMC referral process. In **block one**, we will introduce IHE which will then be maintained throughout the implementation period. Clinic escorts combined with IHE in **block two**. **Block three**, IHE, clinic escorts and SMS tracing will be combined. In **block four**, all intervention components will be combined including transport reimbursement to form the full intervention. Supportive supervision and constructive feedback will be maintained throughout the implementation period. Based on the sample sizes detailed below, we anticipate that each intervention block will last about 3-4 weeks.

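### Objective 1 compares a crude uptake proportion between sequential blocks without a common follow-up window, so the SOC contrast depends on an unstated register closing rule

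*Combined protocol and SAP*

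**What the plan says.** Section 6.3 (Sample Size Calculation and Justification), Data Analysis, Objective 1, defines uptake as "the number of men who will undergo VMMC divided by the number of uncircumcised men offered VMMC at the STI clinic". It adds "Uptake will be calculated for each implementation block" and compares each block with SOC by a t-test. No number of days is attached. Section 4 defines uptake only as undergoing VMMC, but defines time-to-uptake as "the number of days from the day a participant is offered VMMC to the day they undergo VMMC", so the plan already has a time origin. Objective 1a uses Kaplan-Meier curves and Cox regression, without a stated censoring date.

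On timing:

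- Section 6.6.2 (Full implementation) puts SOC first and the full combination in block four. It says "There will be one week of no intervention between interventions as a wash-out period" and "we anticipate that each intervention block will last about 3-4 weeks".
- Section 6.2 (Study setting): "Men with symptomatic STIs will not undergo VMMC on the same day of their STI clinic visit until they complete treatment". Section 6.6.1 (Clinic Escorts): "Men may either undergo same day VMMC (if asymptomatic) or have an appointment for VMMC on a later date if symptomatic".
- Section 6.2 (Data Collection) has registers read daily but does not say when reading stops.
- Section 5.4.1 gives May to October 2020 for the study. Section 6.3 (Study population) gives April to September 2020 for clinic visits. Neither is called a register closing date.

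**The concern.** A crude proportion is comparable between groups only if every man has had the same time in which to be circumcised. Here delay is part of the pathway, because symptomatic men cannot have the procedure on the visit day, and the order of the groups is fixed. The first group (SOC) and the last (full RITE) form the main contrast.

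The text allows at least two closing rules, and they act differently:

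- **One close for all blocks.** Block four has the least follow-up. If the close comes soon after block four, full-RITE uptake is understated.
- **Each block closed at its own end.** Blocks of equal length and equal waiting time show no bias in the ratio when true uptake is the same. However, events are lost in every block, and a block that only shortens the wait appears to raise uptake.

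The text also does not say whether a man counts in the block of his offer or of his procedure. Block of offer is the natural reading, but it matters for procedures that fall in a wash-out week or a later block. While the rule is open, the main result depends on a choice that could be made after data are seen.

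**Working it through.** **Plan's own figure.** The only count for Objective 1 is 2280 men. It reproduces: 27 x (1 - 0.28) = 19.4, taken as 19 per day; 19 x 20 clinic days = 380 per month; 380 x 6 = 2280. It counts visits over six months and sets no follow-up. The plan gives no uptake rate or waiting time to reproduce.

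**Follow-up gap.** This runs from the end of SOC to the end of block four, using section 6.6.2:

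- Shortest: 4 x 3 weeks + 3 wash-out weeks = 15 weeks.
- Longest: 4 x 4 weeks + 4 wash-out weeks = 20 weeks.

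Under one close this is the extra follow-up of the last SOC man over the last block-four man, whatever the closing date. The size of the bias, however, is set by the tail after block four.

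**Capture under a single close.** Assumptions: offers uniform over a block of L = 21 or 28 days; exponential wait from offer among men who are eventually circumcised, with median M; registers close T days after block four. With m = M / ln 2,

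capture = 1 - (m/L) x [2^(-T/M) - 2^(-(T+L)/M)].

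Example with M = 14 (m = 20.2) and T = 28:

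- L = 21: 1 - 0.962 x (0.250 - 0.088) = 84.5%
- L = 28: 1 - 0.721 x (0.250 - 0.0625) = 86.5%

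| Tail after block four | M = 7 days | M = 14 days | M = 21 days |
|---|---|---|---|
| None (outer bound) | 58-66% | 38-46% | 28-35% |
| 28 days | 97-98% | 84-87% | 71-74% |
| 31 days (visits end in September, registers read through October) | 98% | 87-88% | 74-77% |
| 56 days | 100% | 96-97% | 89-90% |

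Even with no tail, SOC capture is 99.7-99.9% at M = 14 and 97.7-99.4% at M = 21.

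At M = 14 and a 28-day tail, equal true uptake reads as a RITE/SOC ratio of 0.85-0.86, and a true ratio of 1.5 reads as 1.27-1.30. At 56 days the figures are 0.96-0.97 and 1.44-1.45. The result also moves with the shape of the wait. At M = 14 and 28 days, capture is 89-91% if 30% of procedures are same-day, and 78-81% if a fixed 7-day lag comes first.

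**Each block closed at its own end (T = 0).** Suppose eventual uptake is equal and the wait is 14 days under SOC and 7 days under RITE (medians). The ratio is 57.9/37.8 = 1.53 for 3-week blocks and 66.2/45.9 = 1.44 for 4-week blocks. With equal waits it is 1.00.

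**Fixed window of W days from offer.** Capture = 1 - 2^(-W/M). If waits are equal, the ratio is unbiased at any W. If the wait halves from 14 to 7 days at equal eventual uptake:

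| W (days) | Captured, M = 14 | Apparent ratio |
|---|---|---|
| 7 | 29.3% | 1.71 |
| 28 | 75.0% | 1.25 |
| 42 | 87.5% | 1.13 |
| 56 | 93.8% | 1.06 |
| 84 | 98.4% | 1.02 |

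**Calendar.** SOC (assumed one block long), four blocks and 3-4 wash-out weeks take 5 x 3 + 3 = 18 to 5 x 4 + 4 = 24 weeks. A 28-day window then ends in week 22-28 and a 56-day window in week 26-32, or four weeks later if the preparatory stages count. Section 6.3 expects about 6 months.

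**The case against.** Five arguments run the other way.

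1. **Waits may be short.** Section 6.1 (Study design) describes STIs as generally acute and quick to resolve with treatment, and section 5.2 expects more uptake within seven days of exposure. At a 7-day median, a four-week tail already captures 97-98%. Both passages are hints; neither gives a waiting time.
2. **A close with no tail is unlikely.** Block-four men who defer receive a coupon, and the procedure is confirmed in the VMMC clinic's "procedures register before payment". Later block-four procedures therefore trigger a register check. This stands, and it is why the no-tail row is only an outer bound. It does not fix a closing date.
3. **Objective 1a covers the same event.** Kaplan-Meier curves from date of offer handle unequal follow-up once a censoring date is stated. The Objective 1 proportion and its t-test do not.
4. **A fixed window has its own distortion.** If RITE halves the wait from 14 to 7 days at equal eventual uptake, a single close with a four-week tail gives 0.975-0.98, nearer to 1 than a fixed window of 56 days (1.06) or 28 days (1.25). This stands as a reason to prefer a longer window. With equal waits the comparison reverses: at a 14-day median the single close gives 0.85-0.86 and the fixed window 1.00.
5. **The rule may be in an appendix.** The data forms (Appendices 3 and 4), the methods summary (12) and the timeline (19) are not in the supplied text. The point is limited to what was supplied.

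A reader might infer that full-RITE uptake will be understated unless registers are read for several weeks after block four. The documents do not support that. The closing rule is not given, closing each block at its own end can favour RITE, and the tail needed depends on an unknown wait.

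**Conclusion.** The point holds as a gap in the definition of the main outcome, without a fixed direction. In the supplied text Objective 1 has no window, closing date or censoring date, while the design puts 15-20 weeks between the last SOC man and the last block-four man. The consequence ranges from negligible (a 7-day median with a tail of four weeks or more) to material (a true ratio of 1.5 read as 1.27-1.30 at a 14-day median with a four-week tail), and it can also inflate the ratio (1.44-1.53) under per-block closing. All these sizes rest on assumed exponential waits and uniform entry. Only the block lengths, wash-outs and order come from the plan. It should be fixed before any block is compared with SOC, because an equal window removes the dependence on block order and uses dates that are already collected.

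**What to change.** In section 6.3, Data Analysis, Objective 1:

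- Count each man in the block of his offer, including when the procedure falls in a wash-out week or a later block.
- Define uptake as VMMC within one fixed number of days from offer, the same for SOC and every block. Make it long enough to cover the plan's own deferral, and set it before any block is compared with SOC. Equivalently, compare Kaplan-Meier cumulative uptake at that day, using the Objective 1a data. Fifty-six days is an example.
- Continue the daily register extraction until the last block-four man completes the window, and use that date as the censoring date for Objective 1a.
- Report the difference from SOC with a 95% confidence interval, and show the Kaplan-Meier curves beside it. A 7-day proportion can serve the section 5.2 hypothesis as a secondary measure of speed.

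If an appendix already states a window or closing date, carry it into this section.

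**Cost.** A wording change plus register extraction for the length of the window. A 56-day window may run past the six months planned. Procedures after the window are not counted: at 56 days, 6% are missed at a 14-day median and 16% at 21 days. Any finite window still partly reflects speed, so a longer one is preferable where the calendar allows.

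### The block-versus-SOC t-test on uptake names no unit of analysis; if read as one value per man, its intervals are too narrow if men sharing a session or clinic day respond alike

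*Combined protocol and SAP*

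**What the plan says.** Section 6.3 Sample Size Calculation and Justification (Data Analysis, Objective 1) defines uptake as a proportion: "the number of men who will undergo VMMC divided by the number of uncircumcised men offered VMMC at the STI clinic". It is calculated once per block. The analysis follows: "Uptake for each block will be compared against SOC using Student's T-test", at a 5% "significance level and 95% confidence interval, assuming normal distribution". The text does not say whether the test is run on men, sessions, days or blocks. No ICC, design effect, clustered standard error or mixed model appears here, or in the Cox and logistic models of Objectives 1a and 1b.

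The delivery of the education is described elsewhere. Section 6.2 Study setting says: "About two to three GHE sessions are conducted per day with different cohorts of patients based on their time of arrival". The intensified education is to be built into these group sessions. Under standard of care (SOC), "only one GHE includes education on VMMC"; in the blocks, Section 6.6.1 Composition promises more than one VMMC talk a day but no exact number. The approach to each man comes later: "After the group education, men will be asked of their interest in circumcision individually". Section 6.6.2 Implementation keeps the education in all four blocks, and Section 5.3 describes the sessions as interactive and aimed at peer support.

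**The concern.** A t-test needs replicate observations. With one proportion per block there are none, so no standard error can be formed. The test becomes computable if each man contributes a 0 or 1, but then it assumes that one man's decision says nothing about another's. Men in one session share the speaker, the talk and the discussion. Men attending on one day share counsellors, clinicians, escorts and the VMMC clinic's capacity that day. If such men tend to decide alike, a block holds less information than its head count suggests.

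All four comparisons with SOC use this standard error. If it is too small, a run of good or poor clinic days can pass for the effect of a component.

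**Working it through.** **1. Reproduce the plan's flow.** Inputs from Section 6.3: 27 men a day, 28% circumcised.
- 27 × (1 − 0.28) = 19.4, stated as 19 a day.
- 19 × 20 clinic days = 380 a month, and 380 × 6 = 2280. Both match the plan.

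**2. Cluster sizes.**
- By session: 19/3 = 6.3 to 19/2 = 9.5 men.
- By day: 19 men.
- A block of 3–4 weeks (Section 6.6.2), at an assumed 5 clinic days a week, has 15–20 days and 285–380 men. The length of the SOC period is not stated and is taken as similar.

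**3. Error of a test that ignores clusters.** Design effect DE = 1 + (m − 1) × ICC. True two-sided error = 2 × (1 − Φ(1.96/√DE)). The plan does not state sidedness; two-sided is assumed because the test is paired with a 95% interval. The ICC range is an assumption.

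| Cluster (m) | ICC 0 | ICC 0.01 | ICC 0.02 | ICC 0.05 |
|---|---|---|---|---|
| Session, 6.3 men | DE 1.00, 5.0% | DE 1.05, 5.6% | DE 1.11, 6.2% | DE 1.27, 8.2% |
| Session, 9.5 men | DE 1.00, 5.0% | DE 1.09, 6.0% | DE 1.17, 7.0% | DE 1.43, 10.1% |
| Day, 19 men | DE 1.00, 5.0% | DE 1.18, 7.1% | DE 1.36, 9.3% | DE 1.90, 15.5% |

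A correct interval is wider by √DE. At ICC 0.05 that is 13–19% by session and 38% by day.

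**4. Check by simulation.** Beta-binomial data, no true difference, 20,000 runs per setting.
- Sessions (20 days, three sessions of 6 or two of 10 men, uptake 5%, 10% and 20%): the individual-level t-test rejected in 5.3–6.0% of runs at ICC 0.01 and 7.7–10.5% at ICC 0.05.
- Days (15–20 days of 19 men, uptake 8% and 15%): it rejected in about 7%, 9–10% and 15–16% at ICC 0.01, 0.02 and 0.05. An unequal-variance t-test on the daily proportions stayed near 5% (roughly 4.5–5.1%), including at ICC 0.

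**5. What the upper figures require.** The SD of the true daily uptake probability is √(ICC × p × (1 − p)). At ICC 0.05 and 8% uptake this is √(0.05 × 0.08 × 0.92) = 6.1 percentage points. At 15% uptake it is √(0.05 × 0.15 × 0.85) = 8.0 points. These are large swings for one clinic.

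**6. Sensitivity to patient flow.** Section 6.2 Study setting gives 80 patients a day; Section 6.3 gives 60. With the same shares, 80 × 27/60 × 0.72 = 25.9 uncircumcised men a day, or 8.6–13.0 per session. At ICC 0.05 the session design effect is then 1.38–1.60 and the error about 10–12%.

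**The case against.** The strongest reply is that the harm is conditional. The documents give no ICC; at zero the planned error is 5.0%, and at 0.01–0.02 by session it is only 5.6–7.0%. Each man is approached individually after the talk, and escorts, text messages and reimbursement act on individual men, which may dilute any session effect. The denominator is men offered VMMC, and Section 6.2 Study setting admits that the offer is not reinforced under SOC, so real clusters may be smaller than the flow suggests. The unit is also inferred: Section 6.2 Data Collection has the data collated daily, so the authors may intend a t-test on daily proportions.

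All of this stands as a limit on certainty. It does not supply the missing unit. Nothing in the analysis text mentions a daily proportion, and staff shared on one day are themselves a reason for day-level correlation.

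Four stronger readings are tempting and not supported.
- A reader might infer that the intervals are certainly too narrow. That needs an ICC above zero, which the documents do not show.
- A reader might take the contrast between the one SOC session with VMMC education and the others as proof of clustering. It is a fixed difference repeated daily, not random variation. With assumed uptake of 15% and 5% in two equal sessions, the mean within-session variance is (0.1275 + 0.0475)/2 = 0.0875, against 0.10 × 0.90 = 0.09 pooled. The simple test would be slightly conservative.
- A reader might fault the equal-variance assumption of Student's test. With no true difference the variances are equal, and with equal block sizes the pooled and unequal-variance standard errors coincide. The point does not rest on this.
- A reader might conclude that VMMC education is given two to three times a day. That count is for group sessions in general.

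**Conclusion.** The plan leaves the unit of its primary test unstated, and the natural reading ignores the shared sessions and clinic days through which the intervention is delivered. The direction is clear for any positive correlation; the size is not known. On the flow of 19 men a day and an assumed ICC of 0 to 0.05, the true error of a nominal 5% test is 5.0–10.1% by session and 5.0–15.5% by day, with the top of each range the least secure. The larger patient flow in Section 6.2 Study setting would raise these figures.

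This should be fixed, with medium confidence, as a cheap improvement. It is not evidence that the trial's conclusions would be wrong.

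**What to change.** In Section 6.3 (Data Analysis, Objective 1), name the unit of analysis and replace the t-test. Report each block-versus-SOC comparison as a risk difference with 95% confidence interval, from one model with block as a factor and standard errors clustered on clinic day of offer. Apply a small-sample correction, since a block has only about 15–20 days. A simpler alternative is an unequal-variance t-test on daily uptake proportions. Sessions lie within days, so clustering on day covers both. Use the same clustering in the logistic and Cox models. Reconcile the 60 and 80 patients a day, because cluster size depends on them.

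The date of offer is already collected for Objective 1a (Section 6.2 Data Collection), so no new data or extra men are needed. The cost is SAP wording and somewhat wider intervals. The change does not deal with calendar time: each condition runs once, in its own period, and the plan itself lists seasonality as a limitation. Day-clustered intervals would still attribute a period difference to the component.
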